The past few years have seen increasing educational efforts and community awareness of the importance of PrEP in preventing HIV infection among MSM and we expect to see increased uptake of this prevention modality over the course of this trial. For self-selected participants under active medical care, PrEP can be very effective [91].

Consistent with this approach, Gilead Sciences has agreed to provide Truvada as PrEP for trial participants at no drug cost to them for the duration of their trial participation. This will be accomplished through the HVTN 704/HPTN 085 PrEP Referral Program in North America for US participants. This program integrates PrEP into the care provided by participants' primary health care provider, ensuring that appropriate screening assays are performed and that drug interactions are monitored over time. Outside the US, participants will participate in PrEP demonstration projects in Peru and Brazil, countries in which Truvada is not yet licensed for HIV prophylaxis but where such demonstration projects are being encouraged. In Switzerland, the CRS will directly provide Truvada at no drug cost to interested participants. In this way, PrEP access will be provided to all participants in the trial and counseling about its availability will be provided as part of HIV risk reduction counseling, which is conducted at all infusion visits throughout the course of the study. This approach has been reviewed and approved by multiple stakeholders, including community members, medical ethicists, multiple IRBs, and the HVTN 704/HPTN 085 DSMB.

As discussed in Sections 4.10 and 9.6, periodic population-based evaluation of PrEP usage will be conducted during the course of the trial. The sample size and power calculations (see Section 4.6) and plans for trial monitoring by the DSMB (see Section 4.9 and, specifically, Section 4.9.3) have been designed to accommodate substantial PrEP uptake. If the background HIV incidence rate is too low to support evaluation of VRC01 prevention efficacy due to high PrEP uptake and adherence, these data will be made available to the DSMB, which will make recommendations to the team accordingly.

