4.4 Statistical rationale for the 3-arm design compared to a 2-arm design

An alternative design would compare a single dose and schedule of the VRC01 mAb versus control. However, the 3-arm design allows addressing additional scientific questions and improves the assessment of correlates of protection, without requiring more participants by virtue of the primary analysis being based on the pooled mAb groups versus control. Specifically, consider a 2-arm design with 2:1 allocation to a single dose of VRC01 versus placebo, compared to the 3-arm design in the protocol with 1:1:1 allocation. For scenarios where the average of PE10 and PE30 equal PE set to a number greater than 0 and less than 1, power to reject H0: PE $\leq 0\%$ in favor or H1: PE > 0% is very similar between the two trial designs, for the same total number of study participants. By providing results about estimated PE10 and estimated PE30 as well as about pooled estimated PE, the trial provides data for modeling of how PE would change given a new dose and/or schedule.

A second advantage of the 3-arm design is that it allows a direct assessment of the causal effect of different mAb infusion doses on HIV-1 incidence based on randomization of treatment assignments (a so-called 'group-level' correlate of protection), which can directly prove the concept that a higher mAb dose causes a greater level of protection. In contrast, with a 2-arm design the association between mAb marker characteristics and the level of PE can only be inferred with non-randomized epidemiological analysis approaches for which the results cannot be guaranteed to be free from postrandomization selection bias [112,113]. That is, without a randomization to multiple mAb interventions a result that a mAb characteristic is associated with reduced incidence of HIV-1 infection may not imply that mAb recipients with the characteristic have a higher level of PE. For instance, the implication may fail if participants tend to have fewer HIV-1 exposures during the few weeks after infusion visits compared to during the few weeks before infusion visits, which could possibly occur related to the counseling and informed consent process. Or, the implication may fail if the mAb characteristic marks an intrinsic

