4.13.7.3 A time-window approach to assessing mAb correlates of protection

To explain the concept of this approach, first suppose all participants received all scheduled infusions and rigidly followed the visit schedule. Then this approach compares HIV-1 incidence during the first 4 weeks of the infusion intervals (ie, weeks 1-4, 9-12, 17-20, ..., 73-76) to HIV-1 incidence during the second 4 weeks of the infusion intervals (ie, weeks 5-8, 13-16, 21-24, ..., 77-80), aggregating over the ten 8-week infusion intervals. Because the mAb has much higher concentration during the first halves of the infusion intervals compared to the second halves (eg, demonstrated in Figure 2-9), detection of higher HIV-1 incidence in the second halves of visit windows would imply that higher concentrations are associated with a lower rate of HIV-1 infection.

However, because of missed infusions and the heterogeneity among participants of infusion dates (which is allowable as specified by broad visit windows), a better approach accounts for the set of exact infusion dates of each participant. As such, our approach to implementing the time-window approach compares the mean time between the last infusion and infection for VRC01 group cases, with the mean of the participant-specific weighted average time between infusions of VRC01 group control participants, where the weights allow for changing HIV-1 incidence over time. The analysis stratifies by the 10 mg/kg and 30 mg/kg dose groups and aggregates estimates over these two dose groups. In addition, an important element of the analysis uses predictions of the HIV-1 infection times for all VRC01 group cases. Models for these predictions are built using information on HIV-1 diagnostic tests, intra-host diversity of HIV-1 sequences, HIV-1 viral loads, and perhaps other factors. Initial research to build predictors of HIV-1 infection time based on HIV-1 sequence information has been conducted using validation data sets of acutely HIV-1 infected individuals [127].

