A related approach to assessing correlates of protection integrates a pharmacokinetic model of the serum concentration of VRC01 over time, comparing the mean VRC01 concentration at the time of HIV infection for VRC01 group cases with the mean of participant-specific weighted average VRC01 concentrations over follow-up time. The participant-specific average VRC01 concentration over follow-up time is intended to reflect the expected concentration at the time of a random HIV exposure, with weighting used as above to allow for changing HIV-1 incidence over time. Details of these statistical methods will be provided in the statistical analysis plan.

4.13.7.4 mAb markers

For effector function markers measured based on a sample from a mAb recipient, the markers are measured to each of a panel of HIV-1 Envelope proteins. The most relevant HIV-1 Env panel represents the VRC01 antibody footprint diversity of viruses exposing trial participants. For example, relevant for the study population of North/South American MSM + TG, Figure 4-8 shows a logo plot of the VRC01 antibody footprint motifs comprising 35 amino acid sites [128,129] based on 276 subtype B US and South American sequences deposited in the Los Alamos National Laboratory (LANL) sequence database between 2006 and 2014. There are 272 unique mAb footprints.

Figure 4-8 Logo plot of the VRC01 antibody footprints that occur in 276 subtype B US and South American sequences deposited in the LANL sequence database between 2006 and 2014

During the conduct of the trial the research team will determine a minimal set of Envs constituting a panel capturing most of the VRC01 mAb footprint diversity of exposing viruses. One effector function marker of interest for assessing as a correlate of protection is the weighted area under the magnitude-breadth neutralization curve of the mAb footprint Env panel, where the weighting is by the estimated prevalence of mAb footprints in HIV-1s circulating at the trial sites during the trial.

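### The time-since-infusion correlates contrasts use VRC01 recipients only, so a dip in exposure after infusion visits, if there is one, could be read as a concentration effect; a placebo negative control would guard against this

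*Protocol*

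**What the plan says.** Protocol Section 4.13.7.3 describes two analyses for secondary objective 1.

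- **Timing version.** It "compares the mean time between the last infusion and infection for VRC01 group cases, with the mean of the participant-specific weighted average time" in a comparison group, measured from one infusion to the next. That group is called control participants, but it consists of uninfected people assigned to VRC01, not placebo recipients. The analysis is stratified by dose and aggregated over the two doses. The reference mean is weighted, "where the weights allow for changing HIV-1 incidence over time".
- **Pharmacokinetic version.** It works by "comparing the mean VRC01 concentration at the time of HIV infection for VRC01 group cases" against a weighted average concentration over follow-up. That average is meant to stand for the concentration at a randomly timed exposure.

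The same section gives the intended reading: "detection of higher HIV-1 incidence in the second halves of visit windows would imply that higher concentrations are associated with a lower rate" (meaning the infection rate).

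Section 4.4 of the protocol names a way in which such inference can break down, namely when "participants tend to have fewer HIV-1 exposures during the few weeks after infusion visits compared to during the few weeks before infusion visits". It also suggests a mechanism, describing the dip as something "which could possibly occur related to the counseling and informed consent process". The safeguard offered there is randomisation to two doses.

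On the schedule, Section 2.5.3 says that PrEP availability is covered in "HIV risk reduction counseling, which is conducted at all infusion visits throughout the course of the study". Between screening and Week 104, Appendix J marks risk-reduction counselling at infusion visits only.

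**The concern.** VRC01 concentration is highest just after an infusion and falls over the following 8 weeks. If counselling lowers exposure for a few weeks, infections will cluster late in the interval for that reason alone. A contrast confined to VRC01 recipients cannot separate the two explanations, because both run on the same clock.

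The safeguard in Section 4.4 does not reach this analysis. Randomisation to dose protects a comparison between doses, whereas the contrasts in 4.13.7.3 stratify by dose and use timing within arm. The weights are described only as handling incidence that changes over time. Their source and resolution are not given, and a within-interval cycle is not mentioned.

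What is at stake is a false correlate of protection under secondary objective 1. The primary efficacy analysis is not affected.

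**Working it through.** **1. Case numbers.** Inputs from Protocol Sections 4.6.1 and 4.6.4: 900 control and 1800 VRC01 participants, control incidence p = 0.03 per year, PE 60% (so p = 0.012 on VRC01), dropout d = 0.10 per year, 80 weeks of follow-up.

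Expected cases = N × p/(p+d) × [1 − exp(−(p+d) × 80/52)]

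- Control: 900 × 0.03/0.13 × (1 − e^−0.200) = 37.6 (protocol: 37).
- VRC01 pooled: 1800 × 0.012/0.112 × (1 − e^−0.172) = 30.5 (protocol: 30).

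The protocol's figures are reproduced; 37 and 30 are used below.

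**2. False-positive rate with no concentration effect.** Let r be the ratio of exposure in the second 4 weeks to exposure in the first 4 weeks of an interval. The documents give no value, so r is an assumption shown over a range. PE is flat across the interval.

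For infection times spread over 56 days, the second-half share is r/(1+r) and the mean time since infusion is [14 + 42r]/(1+r).

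- r = 1.5: share 0.60, mean 30.8 days, a shift of 2.8 days from the mid-point of 28.
- r = 2: share 0.667, mean 32.7 days, a shift of 4.7 days.

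Hand check at r = 1.5: variance = 28²/12 + 28² × 0.6 × 0.4 = 65.3 + 188.2 = 253.5; SE with 30 cases = √(253.5/30) = 2.91; 2.8/2.91 = 0.96, so a two-sided 0.05 test rejects in about 16% of trials.

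| r (assumed) | VRC01 only, mean time (40,000 simulations) | VRC01 only, half-interval Wald | VRC01 minus placebo, mean time |
|---|---|---|---|
| 1.0 | 5% | 5% | 5% |
| 1.25 | 8% | 9% | 5% |
| 1.5 | 16% | 19% | 5% |
| 2.0 | 37% | 43% | 5% |

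The mean-time column is closer to the planned statistic; the half-interval split is only the protocol's way of explaining the idea. The simulation treats the VRC01 non-case reference as known at 28 days and ignores dose strata and irregular infusion dates.

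**3. What the placebo contrast costs when r = 1.**

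- Standard-error ratio: √[(1/30 + 1/37)/(1/30)] = √(1 + 30/37) = 1.35. On the half-interval log-rate-ratio scale, SE goes from 0.365 to 0.491.
- Power, half-interval Wald, for assumed PE in the first and second halves: 70/50%, 27% to 18%; 75/45%, 52% to 34%; 80/40%, 74% to 54%; 85/35%, 88% to 73%.
- Power, mean-time simulation: 45% to 27% at a second/first-half rate ratio of 2.2 (the 75/45% case); 70% to 45% at 3.0 (the 80/40% case).

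The loss is therefore about 10 to 20 points on the first statistic and about 17 to 25 points on the second.

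**The case against.** The strongest reply is that placebo-referenced analyses already exist. Protocol Section 4.13.7.2 defines PE(S(t) = s) against the control-arm hazard and bases the formal correlates test on it. SAP Section 8.2 plans a Cox analysis in the MITT cohort, hence with placebo included, on time from the most recent infusion to estimated infection. Its fit diagnostics include a proportional-hazards test, which on that time scale is in effect a treatment-by-time-since-infusion interaction. A cycle shared by the arms cancels in that hazard ratio. The randomised comparison of the two doses is also unaffected.

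This stands, and it rules out one reading: a reader might infer that secondary objective 1 as a whole ignores the placebo arm. It does not. But the Cox analysis is aimed at detecting PE, with within-interval variation appearing only as a model check. Neither analysis corrects the 4.13.7.3 contrasts or is tied to their interpretation.

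Other replies also carry weight:

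- **The cycle is conjecture.** Section 4.4 raises it only as a possibility. Every 4-weekly visit includes HIV pre-test counselling with post-test follow-up (Section 7.4; Appendix J, footnote 4), so counselling contact is not purely 8-weekly.
- **Placebo may not cancel everything.** Protocol Section 8.4 and SAP Section 5.2 warn that VRC01 could suppress replication or alter serological response. Error in dating infections could then differ by arm.
- **The wording is associational, and details are deferred.** Section 4.13.7 is a summary, and SAP Section 2.2 points to a separate correlates plan that was not available. Both the absence of placebo data and the scope of the weights may be settled there.

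**Conclusion.** The gap is real but limited. As written, the 4.13.7.3 contrasts cannot distinguish a concentration effect from an exposure dip after infusion visits, and the section gives its interpretation without the caveat in Section 4.4. If exposure were 1.5 or 2 times higher in the second half of the interval, the VRC01-only mean-time test would be positive in about 16% or 37% of trials with no concentration effect. At 1.25-fold it would be 8%.

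These figures rest on 30 VRC01 cases, flat PE and an assumed exposure ratio. The return to 5% with placebo also assumes that the behavioural cycle is the same in every arm, which blinding supports but does not prove.

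Three stronger conclusions might be drawn, and the documents do not support them. They do not show that exposure does cycle with infusions. They do not show that a placebo correction is free, since it costs power. And they give no ground for demoting the VRC01-only result to a purely descriptive one: with no cycle it is the more powerful test. This is a cheap improvement to a secondary analysis.

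**What to change.** In Protocol Section 4.13.7.3 and the Correlates of Prevention Efficacy SAP:

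- Pre-specify the same time-since-last-infusion analysis in the placebo arm as a negative control. For the pharmacokinetic version, use concentrations predicted from placebo recipients' own infusion dates.
- Report the VRC01-minus-placebo difference beside the VRC01-only result, and attribute a VRC01-only signal to concentration only if the placebo comparison supports it.
- Cross-refer to PE(S(t) = s) in Protocol Section 4.13.7.2 and to the time-since-infusion Cox analysis in SAP Section 8.2.
- State the source and time resolution of the weights.

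**Cost.** No new participants, samples or assays: placebo recipients are infused on the same schedule, and SAP Section 5.4 already estimates infection dates for everyone diagnosed. The plan should state the downsides openly: the loss of precision and power shown above, the assumption of a common behavioural cycle across blinded arms, and the possibility that dating error differs by arm and so remains. If the correlates SAP already contains this analysis, a cross-reference in 4.13.7.3 is enough.

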4.13.7.5 Statistical power for assessing a mAb marker as a correlate of protection

The marker S(t) must vary within mAb recipients over time and/or among mAb recipients in order to detect a correlate of protection, with more variability in one or both components providing greater statistical power to detect a correlate of protection via testing the null hypothesis of equation/panel (1) above. In essence, to detect correlates of protection it is necessary that a large fraction of person-years at risk are in high protection zones and a large fraction of person-years at risk are in low protection zones. (A "high protection zone" is a period of time during which a mAb recipient has high levels of a marker and high levels of efficacy.) Data from VRC 601, VRC 602, and HVTN 104 show wide variability in the mAb concentration over time, and more limited variability among mAb recipients. HVTN 104 will provide more data on these two aspects of marker variability. The limited among-mAb recipient variability motivates the study design that randomly assigns participants to 2 different mAb doses in order to create inter-individual variability.

[figure not shown]
Achieving adequate power to detect correlates of protection requires that the HIV-1 diagnostic testing is more frequent than the infusion schedule. This is why diagnostic visits every 4 weeks are advantageous given infusions every 8 weeks, and procedures may be determined and applied to test for HIV-1 infection more frequently than every 4

weeks. The data from all of the employed diagnostic testing kits is incorporated into the modeling of S(t) and of HIV-1 infection times, and is integrated into the modeling of S(t) and into the statistical analysis for estimation and testing of PE(S(t) = s). Lastly, achieving adequate power to detect correlates of protection requires studying markers that can be measured with a high ratio of potentially protection relevant variability versus protection irrelevant variability, where the latter variability could stem from technical measurement error of the assay or to error in estimation of the timing of infection. Because of this fact the trial design relies on parallel assay studies to qualify marker variables for the analysis and relies on development and characterization of models for S(t) over continuous time t.

Figure 4-9 shows power curves for the scenario that (30%, 40%, 30%) of PYRs at risk are in the (Low, Medium, High) zones (which we approximately expect to occur based on Figure 2-4) and PE10 = PE30 = (15%, 60%, 85%) in these zones. The power curves also account for noise in the measurement of S(t) via a parameter rho that equals the proportion of the inter-individual marker variability that is potentially protection relevant. The results show that the noise level majorly affects power, underscoring that only assays meeting qualification criteria will be studied as correlates. The parameter rho also reflects noise due to uncertainty in the exact times t of HIV-1 acquisition at which values of S(t) are needed. For the scenario that this extra variability reduces rho to 0.7, there is about 70% power to detect a correlate of protection (with effect size 15%, 60%, 85% efficacy) at the selected trial sample size. Note that the parameter rho also reflects noise due to uncertainty in the exact times t of HIV-1 acquisition at which values Of A more extensive set of power calculations will be conducted based on HVTN 104 study data.

[figure not shown]

Power to Discriminate (Lo, Med, Hi) PE = (15%, 60%, 85%) [Overall PE = 60%] 30% with Lo and 30% with Hi Marker Response

2-phase logistic regression; 2-sided alpha = 0.05; controls:cases = 5:1

Figure 4-9 Power of the trial for detecting that PE varies over the three mAb marker-defined subgroups S(t) = Low, S(t) = Medium, and S(t) = High at level PE=15%, 60%, 85%, respectively, for a marker with assay noise parameter rho = 1 (perfect marker), 0.9, 0.7, and 0.5 and percentages of person-years at risk in the (Low, Medium, High) marker regions set at (30%, 40%, 30%). The calculations at 2700 total participants assume 30 mAb group HIV-1infected cases and 150 mAb group HIV-1–uninfected controls with data on S(t) and pool over both mAb groups. The dashed vertical line represents the sample size of the study.

Figure 4-10 shows the same power analysis as Figure 4-9, fixing rho = 0.9 (indicating a qualifying assay) and varying the percentage of PYRs at risk that are in the (Low, Medium, High) zones. The results show that power increases sharply with the percentage of mAb recipients that are in the Low and High regions, demonstrating the principle that variability in the marker is a strong determinant of power to detect a correlate of protection. For example, the figure shows that the trial has 80% power for the PE = 15%. 60%, 85% effect size if 25%, 50%, 25% of PYRs at risk are in the (Low, Medium, High) zones.

Power to Discriminate (Lo, Med, Hi) PE = (15%, 60%, 85%) [Overall PE = 60%; rho = 0.9]

[figure not shown]

Figure 4-10 Power of the trial for detecting that PE varies over the three mAb marker-defined subgroups S(t) = Low, S(t) = Medium, and S(t) = High at level PE = 15%, 60%, 85%, respectively, for a marker with assay noise parameter rho = 0.9 and percentages of person-years at risk in the Low and High marker regions varied from 10%, 15%, 20%, 25%, 30%. The calculations at 2700 total participants assume 30 mAb group HIV-1–infected cases and 150 mAb group HIV-1–uninfected controls with data on S(t) and pool over both mAb groups.

4.13.7.6 Genotypic and phenotypic sieve analysis

Genotypic sieve analysis analyzes sequences of breakthrough HIV-1 infecting viruses from the earliest available postinfection sample and seeks to identify amino acid "signatures" that differentiate breakthrough sequences in the mAb groups versus the control group, in terms of differential PE against HIV-1s according to some genotypic characteristics. For example, the genotypic sieve analysis assesses differential PE against different genotypes of HIV-1 with genotype defined by:

- Number of mismatches to the VRC01 mAb footprint of the subtype B consensus sequence (subtype selected to match the circulating HIV-1s)
- Number of known mAb neutralization escape mutations in the mAb footprint
- Number of known mAb effector function escape mutations in the mAb footprint for non-neutralization effector functions such as ADCC, virion capture, and phagocytosis
- Number of potential N-linked glycosylation (PNG) sites within a given radius of the mAb footprint
- Length of variable loops in proximity to the mAb footprint

To illustrate the utility of genotypic sieve analysis, we consider a hypothetical result that would support that the mAb protects via specific neutralization targeting of the mAb's epitope. In this illustration, the HIV-1 genotype is defined by four ordered genotypes according to whether there are 0, 1, 2, or >2 neutralization escape mutations in the VRC01 mAb antibody footprint. The hypothetical result would be an estimated PE of 95% against HIV-1s with zero escape mutations and a PE of 0% against HIV-1s with >2

neutralization escape mutations, and intermediate and monotone decreasing level of estimated PE against HIV-1 with one mutation and two mutations, respectively.

A second type of sieve analysis, phenotypic sieve analysis, compares breakthrough viruses between the mAb versus control groups using an immunological assay. Specifically, data from an "effector function checkerboard" is filled out, with the rows representing serum samples from a random sample of mAb recipients HIV-1 uninfected at the time of sampling, and the columns representing HIV-1 Env VRC01 footprint targets created from the breakthrough viruses. The phenotypic sieve analysis compares the sensitivity of the breakthrough viruses to mAb recipient sera between the mAb and control treatment groups. A second version of the phenotypic sieve analysis compares the sensitivity of the breakthrough viruses to the VRC01 mAb between the treatment groups; this latter analysis is simpler, based on a single column of data instead of a matrix, because it does not use mAb recipient sera. For an example of the second type of phenotypic sieve analysis, the TZM-bl neutralization assay could be performed on all control breakthrough HIV-1s versus VRC01 and on all mAb group breakthrough HIV-1s (pooled over the two mAb groups) versus VRC01, and a Wilcoxon rank sum test applied to assess a difference. Reduced TZM-bl neutralization sensitivity of the mAb breakthrough group viruses would support that neutralization had a role in protection and that the TZM-bl assay was able to detect this role, and would support using the TZM-bl assay as a tool for evaluating future candidate HIV-1 vaccines. The HVTN has previously conducted neutralization sieve analysis [130]. Figure 4-11 illustrates a genotypic and phenotypic sieve analysis.

[figure not shown]

[figure not shown]
Figure 4-11 Illustration of genotypic (left panel) and phenotypic (right panel) sieve analysis, where the left panel shows the distribution of the number of known neutralization escape mutations in breakthrough control and mAb group HIV-1 sequences, and the right panel shows the percentage of the panel of breakthrough HIV-1s that are neutralized at level 50% (IC₅₀) by the given concentration of the VRC01 mAb.

Another phenotypic sieve analysis focuses on mAb group cases, and measures different effector functions of closest-to-infection participant serum samples or of the VRC01 mAb against the participant-matched breakthrough HIV-1s. The effector functions that tend to have low readouts against participant-matched breakthrough viruses compared to against the panel of control group HIV-1s or compared to an historic panel of HIV-1s are implicated as potential correlates of protection.

In addition, an important sieve analysis will assess PE against HIV-1s that are sensitive to neutralization by VRC01 as measured using the first post-infection sample (sensitive is defined by positive neutralization based on IC_{50} or IC_{80}). This PE parameter measuring prevention efficacy against neutralization sensitive HIV-1s is estimated (with confidence intervals and p-values) in the same way as genotype-specific PE described above. In addition, the same hypothesis testing procedure for detecting differential PE by two HIV-1 genotypes is applied for assessing differential PE by neutralization sensitive versus resistant HIV-1. Moreover, this sieve analysis of sensitive versus resist HIV-1 is also conducted with sensitive/resistant defined by positive/negative response of other assays besides neutralization (eg, ADCC, ADCP).

